8.2 Key and Secondary Efficacy Analysis

The key secondary efficacy endpoint is

- Change from baseline in conjunctival redness on a 9-point scale (0-4) during the chamber (approximately 10 to 210 minutes)

The secondary efficacy endpoints are

- Change from baseline in tearing on a 4-point scale (0-3) during the chamber (approximately 10 to 210 minutes)
- Change from baseline in TOSS on an 11-point composite score (sum of itching, tearing, and redness) during the chamber (approximately 10 to 210 minutes)

TOSS will be derived as the sum of ocular itching, conjunctival redness and tearing symptoms at each time point.

Observed and changes from baseline duration treatment EEC session will be summarized by visit and treatment for ITT population.

All secondary efficacy endpoints will be analyzed using a similar approach as the primary efficacy variable for the ITT Population. Reproxalap Ophthalmic Solution will be claimed to be better than Vehicle on secondary efficacy endpoints if the estimated overall corresponding changes from baseline score from MMRM model in the Reproxalap group is statistically lower than that of the Vehicle group during the chamber (approximately 10 to 210 minutes).

[REDACTED]

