## SYNOPSIS

Name of Sponsor Company: Aldeyra Therapeutics, Inc.	Drug Under Study: Reproxalap	
Title of Protocol: The INVIGORATE Trial: A single-center, randomized, double-masked, crossover design, vehicle-controlled, Phase 3 clinical trial to assess the efficacy and safety of reproxalap ophthalmic solution (0.25%) compared to vehicle in subjects with seasonal allergic conjunctivitis using the environmental exposure chamber (EEC).		
Protocol Number: Sponsor Study Code: ADX-102-AC-017  [REDACTED] Study Code: 19-MO-003-B	Phase: 3	Indication: Allergic Conjunctivitis
Subject Population: Subjects 18 years of age and older with allergic conjunctivitis		
Number of Subjects: Approximately 670 subjects with seasonal allergic conjunctivitis to ragweed will be screened in order to randomize approximately 126 subjects, with approximately 100 subjects completing the trial.		
Number of Center(s): One		
Test Products / Doses / Mode of Administration: Eligible subjects will be randomized 1:1 to one of two treatment sequences of AB or BA where: 

Treatment A: Reproxalap Ophthalmic Solution (0.25%)

Treatment B: Vehicle Ophthalmic Solution [REDACTED]

 Approximately 126 subjects (approximately 63 per treatment sequence) will be enrolled.		
Criteria for Evaluation:		
Primary Endpoint: 

Change from baseline in Ocular Itching score on a 9-point scale (0-4) from 110-210 minutes

		
Key Secondary Endpoint: 

Change from baseline in Conjunctival Redness on a 9-point scale (0-4) over the duration of the chamber (approximately 12 to 212 minutes)

		
Secondary Endpoints: 

Change from baseline in Tearing on a 4-point scale (0-3) over the duration of the chamber (approximately 10 to 210 minutes)

Change from baseline in total ocular symptom score (TOSS, sum of itching, redness, and tearing scores) on an 11-point composite score over the duration of the chamber (approximately 10 to 212 minutes)

		
Safety Measures: 

Adverse Events (reported, elicited, and observed)

Snellen Visual Acuity (VA)

Slit Lamp Examination (SLE)

Non-contact Intraocular Pressure Tonometry (NCT), as detailed in Table 1.

		

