#### **Key Secondary Endpoint:**

- Change from baseline in Conjunctival Redness on a 9-point scale (0-4) over the duration of the chamber (approximately 12 to 212 minutes)

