#### **Secondary Endpoints:**

- Change from baseline in Tearing on a 4-point scale (0-3) over the duration of the chamber (approximately 10 to 210 minutes)
- Change from baseline in TOSS on an 11-point composite score (sum of itching, tearing, and redness) over the duration of the chamber (approximately 10 to 212 minutes)

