3.2.2.2 Key Secondary Endpoint

- Change from baseline in conjunctival redness on a 9-point scale (0-4) during the chamber (approximately 12 to 212 minutes)

[figure not shown]

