3.2.2.3 Secondary Endpoints

- Change from baseline in tearing on a 4-point scale (0-3) during the chamber (approximately 10 to 210 minutes)
- Change from baseline in TOSS on an 11-point composite score (sum of maximum score of itching, tearing and redness) during the chamber (approximately 10 to 212 minutes)
- Safety Endpoints
- Ophthalmic examinations
 - Snellen visual acuity (VA)
 - Slit lamp examination (SLE)
 - Non-contact intraocular pressure tonometry (NCT)
 - Dilated fundus examination at screening Visit 1 and at Visit 4
 - Undilated fundus examination at Visits 2 and 3
- Adverse events
- Vital signs
- Clinical laboratory tests

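### Do the differing time windows in SAP section 8 change which readings enter the itching, redness and TOSS analyses?

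*SAP*

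**What the plan says.** **Redness (key secondary).** SAP 3.2.2.2 defines it as "Change from baseline in conjunctival redness on a 9-point scale (0-4) during the chamber (approximately 12 to 212 minutes". The protocol synopsis agrees: "Change from baseline in Conjunctival Redness on a 9-point scale (0-4) over the duration of the chamber (approximately 12 to 212 minutes". So does protocol 2.3. SAP 8.2 restates it as "Change from baseline in conjunctival redness on a 9-point scale (0-4) during the chamber (approximately 10 to 210 minutes".

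**TOSS (secondary).** SAP 8.2 has "Change from baseline in TOSS on an 11-point composite score (sum of itching, tearing, and redness) during the chamber (approximately 10 to 210 minutes". SAP 3.2.2.3 has "sum of maximum score of itching, tearing and redness) during the chamber (approximately 10 to 212 minutes", and the synopsis has "on an 11-point composite score over the duration of the chamber (approximately 10 to 212 minutes". Protocol 2.3 gives the same 10 to 212.

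**Itching (primary).** SAP 8.1 gives 110-212 minutes, without a qualifier. SAP 3.2.2.1, the protocol synopsis (endpoint and analysis text), and protocol 2.3, 10.2 and 10.6 all give 110-210.

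**Tearing (secondary).** About 10 to 210 in every endpoint definition and in SAP 8.2.

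**Analysis text.** The rule in SAP 8.2 for claiming benefit applies about 10 to 210 to the secondary endpoints together. In the protocol, section 10.7 also uses about 10 to 210 for all of them, the synopsis analysis paragraph uses about 10 to 212, and the opening of section 2.3 uses about 10 to 212 for every change from baseline.

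**Data entering the models.** The introduction to SAP section 8 says, for all efficacy endpoints, that the MMRM takes every reading available from the chamber session. Screening-session and post-exit readings are only listed. SAP 2.1 places exit at about 215 minutes.

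**The concern.** Two parts of one SAP give different windows for the primary, key secondary and TOSS endpoints. The protocol (synopsis and section 10.3) makes the SAP prevail on statistical matters, so the protocol cannot simply be used to settle a conflict inside the SAP. The SAP 8.2 window also sits in the sentence that says when reproxalap may be called better than vehicle.

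The definitions appear to separate two kinds of reading on purpose: subject-rated tearing runs from about 10 to 210 and staff-graded redness from about 12 to 212, as if staff grade about two minutes after the subject scores. SAP 8.2 loses that distinction. A programmer who filtered redness literally at 210 minutes would drop the last in-chamber grading, and with it the redness part of the last TOSS value. If the choice were left until after unmasking, it would be a choice about a key secondary endpoint.

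**Working it through.** The question is which readings each window admits. The documents give no numerical result to reproduce, so the stated windows are set side by side.

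| Endpoint | SAP 3.2.2 and protocol definitions (min) | SAP 8.1 / 8.2 (min) | Start shift | End shift |
|---|---|---|---|---|
| Itching | 110-210 | 110-212 | 0 | +2 |
| Redness | about 12-212 | about 10-210 | -2 | -2 |
| Tearing | about 10-210 | about 10-210 | 0 | 0 |
| TOSS | about 10-212 | about 10-210 | 0 | -2 |

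**Itching.** Protocol 10.6 and the synopsis analysis text place the comparisons every 10 minutes from 110 to 210.
- Readings in 110-210: (210 - 110)/10 + 1 = 11.
- Readings in 110-212: the next grid point would be 220, which is beyond 212, so again 11.
- Difference: 11 - 11 = 0.

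**Redness, literal reading.** If 10-210 were applied as a hard filter:
- At the start nothing is lost, because 12 lies inside 10-210.
- At the end only a grading after 210 is lost, so at most one per session (at about 212).
- Over two treatment sessions: 1 x 2 = at most 2 readings per subject.

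The redness schedule (protocol Table 3) is not shown, so the 212-minute grading is inferred from the 12-212 definition. No share of all readings can be given.

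**Redness, reading SAP section 8 as a whole.**
- Every redness window is marked as approximate and tied to the time in the chamber. Both ends move by the same 2 minutes, which fits a nominal label better than a truncation.
- Exit is at about 215 minutes. Since 212 < 215, a grading at about 212 is in-chamber data, which section 8 puts into the model. Only post-exit readings are set aside.
- Readings lost: 0.

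**TOSS.** SAP 8.2 derives TOSS by adding its three components at each time point. If redness is graded about two minutes after itching and tearing, that sum exists only when 210 and 212 count as one nominal time point. A cut between them would contradict the derivation in the same section. Readings lost: 0.

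**The case for a change.** The strongest case for a change is that an endpoint window should be stated once and identically, above all for the primary and key secondary endpoints in the governing document. The general sentence on in-chamber data competes with a specific window in the SAP 8.2 success rule, and a programmer should not have to decide which prevails. Correcting the wording would cost almost nothing.

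Part of this stands. The 110-212 in SAP 8.1 carries no qualifier, occurs once against six places with 110-210, and is plainly a slip. SAP 8.2 does blur the difference between the redness and tearing windows.

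The rest is weaker. For redness and TOSS, calling the SAP 8.2 windows wrong overstates the matter. The protocol's own analysis text is split: section 10.7 uses the same 10 to 210 as SAP 8.2, while the synopsis analysis text and the opening of section 2.3 use 10 to 212. The documents use these figures loosely for one thing, the stay in the chamber. The specific window and the general sentence conflict only if an approximate figure is read as an exact limit. The assessment schedules are not shown and model text in SAP 8.1 and the end of 8.2 is redacted, so the time points may be listed there. The loss of a reading is therefore not shown.

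**Conclusion.** The concern does not call for a change. The wording differs as described, but the same data are analysed under either set of windows: 11 itching readings in both, and no redness or TOSS reading lost once the in-chamber rule of SAP section 8 is applied. The upper bound, under a literal cut that section 8 does not support, is one redness reading per session and two per subject, with the matching redness component of TOSS.

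This rests on three assumptions: readings are selected by nominal time point, as the 10-minute grid in protocol 10.6 implies; the last in-chamber redness grading is at about 212 minutes, before exit at about 215; and the redacted model text does not impose a hard stop at 210. An analyst working from SAP 3.2.2 and section 8 together would reach the same data set. The 110-212 can be tidied if the SAP is reopened for another reason, but no result depends on it.
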